4.6.3 Study Discontinuation

The Sponsor has the right to terminate this study at any time. Reasons for terminating the study may include, but are not limited to, the following:

- The incidence or severity of adverse events in this or other studies indicates a potential health hazard to patients
- Patient enrollment is unsatisfactory

The Sponsor will notify the investigator if the Sponsor decides to discontinue the study.

4.6.4 Site Discontinuation

The Sponsor has the right to close a site at any time. Reasons for closing a site may include, but are not limited to, the following:

- Excessively slow recruitment
- Poor protocol adherence
- Inaccurate or incomplete data recording
- Non-compliance with the International Council for Harmonisation (ICH) guideline for Good Clinical Practice
- No study activity (i.e., all patients have completed the study and all obligations have been fulfilled)

5. ASSESSMENT OF SAFETY

5.1 SAFETY PLAN

MTAU9937A is not approved, and clinical development is ongoing. The safety plan for patients in this study is based on clinical experience with MTAU9937A in completed and ongoing studies. Important potential safety risks for patients receiving MTAU9937A are outlined below. Refer to the MTAU9937A Investigator's Brochure for a complete summary of safety information.

[¹⁸F]GTP1 radioligand is not approved by any health authority, and clinical development is ongoing. The safety plan for participants in this study is based on clinical experience with [¹⁸F]GTP1 radioligand in completed and ongoing studies, and the safety experience to date is detailed in the [¹⁸F]GTP1 Investigator's Brochure.

Several measures will be taken to ensure the safety of patients participating in this study. Eligibility criteria have been designed to exclude patients at higher risk for toxicities. Patients will undergo safety monitoring during the study, including assessment of the nature, frequency, and severity of adverse events. Ongoing review of unblinded safety data will be performed by an IMC (see Section 3.1.2). External experts may be consulted. In addition, guidelines for managing adverse events, including criteria for dosage modification and treatment interruption or discontinuation, are provided below.

5.1.1 Potential Risks Associated with MTAU9937A

5.1.1.1 Infusion-Related Reactions or Hypersensitivity

Monoclonal antibodies such as MTAU9937A may be associated with a potential immune response in clinical trials, such as hypersensitivity or hypersensitivity-like reactions, including severe, anaphylactic reactions (see [Appendix 6](#) for precautions). Study sites will be prepared to manage any hypersensitivity or hypersensitivity-like events.

All participants will be monitored for infusion-related reactions, hypersensitivity, or hypersensitivity-like reactions during the infusion and immediately afterward (see Section 5.1.3.2 for additional instructions on monitoring and management of infusion-related reactions).

5.1.1.2 Neuroimaging Abnormalities

The occurrence of imaging abnormalities believed to represent cerebral vasogenic edema and microhemorrhage have been reported in association with the investigational use of immunotherapy targeting the A β peptide, possibly by interacting with A β deposited in or around blood vessels and eliciting an immune response. Symptoms, when present in association with such imaging abnormalities, have been reported to include headache, worsening cognitive function, alteration of consciousness, seizures, unsteadiness, and vomiting (Salloway et al. 2009; Sperling et al. 2012).

Tau pathology occurs primarily intracellularly in the cytoplasm of diseased neurons (Braak et al. 2006), and soluble extracellular tau is found in the CSF (Blennow and Zetterberg 2009). Unlike A β , tau is not known to deposit in vascular structures, and administration of an antibody against the tau protein is not anticipated to cause vasogenic edema or microhemorrhage. Moreover, MTAU9937A has an IgG4 backbone, which is associated with reduced effector function. Nevertheless, in this study, the following will be performed to monitor for potential neuroimaging abnormalities:

- All patients will have an MRI at screening and at several postbaseline timepoints (see [Appendix 1](#)–[Appendix 4](#)). MRI must be performed prior to any dosing on the corresponding study visit and must be read locally in real time for the evaluation of any new, clinically significant abnormality prior to the dose being given. However, if no such abnormalities are identified in the local MRI interpretation, the dose may be given prior to the receipt of the central MRI report. In case of an abnormality identified by the central MRI reading, the investigator should assess the clinical significance of it and proceed as described below.
- During the COVID-19 pandemic, if study-associated MRIs cannot be obtained, the patient should be monitored for any signs or symptoms suggestive of new, clinically significant neurologic abnormalities. If no new, clinically significant abnormalities are observed, study drug may be administered without an MRI, but a subsequent unscheduled study-associated MRI should be obtained as local conditions allow. If new, clinically significant neurologic abnormalities are observed, study drug should be withheld and the patient should be referred for appropriate follow-up and medical treatment, including, if appropriate, an MRI. Preliminary analyses of *unblinded* safety data from Studies GN39763 and GN40040 suggest that rates of MRI abnormalities in these studies are consistent with background rates reported in this patient population (Carlson et al. 2011; Caunca et al. 2016).
- All patients will regularly undergo neurologic examinations to evaluate for any neurologic signs or symptoms. In case of findings suggestive of a new, clinically significant CNS disturbance or lesion, patients must undergo an MRI examination as soon as possible.
- All MRIs will be read locally in real time for the evaluation of any clinically significant new or worsening abnormality. Study drug will be withheld at the corresponding study visit if, in the investigator's judgment, any clinically significant new or worsening MRI abnormality (e.g., symptomatic or asymptomatic intracranial tumor, cerebral infarct [lacunar or territorial], cerebral hemorrhage [macrohemorrhage, microhemorrhage, superficial siderosis], vasogenic edema, sulcal effusion) is observed. Restarting study drug treatment can occur only after discussion with the Medical Monitor.
- Regardless of severity, all events of a clinically significant new or worsening MRI abnormality that occur at any time after receiving study drug are considered to be adverse events of special interest and must be reported in an expedited manner.

5.1.1.3 Immunogenicity

MTAU9937A is a pan-tau IgG4 monoclonal antibody engineered to contain Fc mutations (YTE) that enhance binding to FcRn and have been shown to slow peripheral antibody clearance in humans. ADAs to MTAU9937A in humans may be associated with changes in MTAU9937A exposure, reductions in treatment efficacy, or safety findings such as hypersensitivity reactions. In the Phase I study (GN39058), there was no evidence of treatment emergent ADAs. Immunogenicity in this Phase II study (GN40040) will be evaluated using validated immunoassays and by assessing the incidence of ADAs after treatment relative to their prevalence at baseline.

5.1.2 Potential Risks Associated with [¹⁸F]GTP1 and Amyloid PET Radiopharmaceuticals

5.1.2.1 Infusion-Related Reactions

All participants will be monitored for infusion-related reactions both during the infusion and immediately afterward. Infusion-related reactions should be treated as per institutional guidelines. In the event that a participant experiences an infusion-related reaction, the infusion should be halted.

5.1.2.2 Radiation Risk

[¹⁸F]GTP1 and amyloid PET radioligands, similar to other radiopharmaceuticals, contribute to a patient's overall long-term cumulative radiation exposure. Long-term cumulative radiation exposure is associated with an increased risk of cancer. Safe handling of [¹⁸F]GTP1 and amyloid PET radioligands should be ensured to protect patients and health care workers from unintentional radiation exposure.

Radiation exposure for [¹⁸F]GTP1 radioligand doses can be found in the [¹⁸F]GTP1 Investigator's Brochure. Radiation exposure for the amyloid tracers can be found in the local labeling instructions or, depending on locality, the Investigator's Brochures. See the local labeling instructions or, depending on locality, the Investigator's Brochure, in addition to consulting with the local PET imaging center for additional radiation exposure due to potential head computed tomography (attenuation correction) scans acquired in conjunction with PET imaging.

Refer to local guidelines for recommended annual radiation exposure.

5.1.3 Management of Patients Who Experience Specific Adverse Events

5.1.3.1 Treatment Interruption

MTAU9937A (or placebo) treatment may be temporarily suspended in patients who experience toxicity considered to be related to study drug. If more than two doses of MTAU9937A (or placebo) have been withheld because of toxicity, the patient should be discontinued from MTAU9937A (or placebo), unless resumption of treatment is approved following investigator discussion with the Medical Monitor.

MTAU9937A (or placebo) treatment may be suspended for reasons other than toxicity (e.g., surgical procedures) with Medical Monitor approval. The investigator and the Medical Monitor will determine the acceptable length of treatment interruption.

5.1.3.2 Management Guidelines for Infusion-Related Reactions

In the event that a participant experiences a mild infusion-related reaction, the infusion may be halted. Once the reaction has resolved, the infusion rate will be resumed at half of the most recently used rate (e.g., from 60 mL/hr [1.0 mL/min] to 30 mL/hr [0.5 mL/min]; see Section 4.3.2.1). Patients who experience a moderate to severe infusion-related reaction (e.g., fever or chills) should have their infusion stopped immediately and should receive aggressive symptomatic treatment. The patient should be monitored until all infusion-related adverse events are Grade 1 or are resolved. The infusion should not be restarted before all symptoms have disappeared, and then it should be restarted at half the initial rate. The infusion should not be resumed if there is a second occurrence at the same visit or if the patient experiences any of the following: mucosal tissue involvement, airway compromise, or symptomatic hypotension with systolic blood pressure <90 mmHg measured in the supine position. In the case of any serious or severe infusion-related reaction, the investigator must discuss with the Medical Monitor whether to continue study drug treatment (see Section 4.3.2.1 for further details).

In the event of an infusion-related reaction, unscheduled ADA and PK serum samples should be collected at the following three timepoints: as close to investigator-determined onset of the event as feasible, at investigator-determined resolution of the event, and 30 days after the resolution of the event.

For patients who experience a serious or severe hypersensitivity or hypersensitivity-like reaction (e.g., hypotension, mucosal involvement), the investigator must discuss with the Medical Monitor whether to continue study drug treatment (see Section 4.3.2.1 for further details).

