
 • Begin infusion at an initial rate of 0.5 mL/min (30 mL/hr). • If no infusion-related or hypersensitivity reaction occurs during the first 30 minutes, then increase the rate to 1.0 mL/min (60 mL/hr). • If no infusion-related or hypersensitivity reaction occurs during the subsequent 30 minutes, then increase the rate to 3.0 mL/min (180 mL/hr). • If a reaction develops, stop or slow the infusion. Administer medications and supportive care in accordance with institutional guidelines. The patient should be monitored until all infusion-related adverse events are Grade 1 or are resolved. 
If the reaction resolves, resume the infusion at a 50% reduction in rate (i.e., 50% of rate being used at the time that the reaction occurred). If the reaction recurs after resumption of the infusion, then stop the infusion. For patients who experience serious or severe hypersensitivity or hypersensitivity-like reactions (e.g., hypotension, mucosal involvement), the investigator must discuss with the Medical Monitor whether to continue study drug treatment.
	
 • If the participant experienced an infusion-related or hypersensitivity reaction during the prior infusion, begin infusion at an initial rate of 0.5 mL/min and follow instructions for first infusion. • If the participant tolerated the prior infusion well (defined by an absence of Grade 2 reactions during a final infusion rate of 3.0 mL/min), begin infusion at a rate of 3.0 mL/min. • If a reaction develops, stop or slow the infusion. Administer medications and supportive care in accordance with institutional guidelines. The patient should be monitored until all infusion-related adverse events are Grade 1 or are resolved. 
If the reaction resolves, resume the infusion at a 50% reduction in rate (i.e., 50% of rate being used at the time that the reaction occurred). If the reaction recurs after resumption of the infusion, then stop the infusion. For patients who experience serious or severe hypersensitivity or hypersensitivity-like reactions (e.g., hypotension, mucosal involvement), the investigator must discuss with the Medical Monitor whether to continue study drug treatment.

OLE = open-label extension.

^a First infusion instructions apply to the first infusion of MTAU9937A or placebo during the double-blind treatment period and the first infusion of MTAU9937A during the OLE period.

4.3.2.2 $[^{18}\text{F}]\text{GTP1}$ Tau PET Radioligand

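### Table 1 and Section 5.1.3.2 give conflicting instructions for restarting an infusion after a moderate to severe reaction

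*Combined protocol and SAP*

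**What the plan says.** Two places in the protocol tell sites what to do when a patient reacts during an infusion of MTAU9937A or placebo.

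**Section 4.3.2.1, Table 1.** Both columns (first infusion and subsequent infusions) carry the same rule, with no distinction by severity. The infusion is stopped or slowed and, if the reaction resolves, sites are to "resume the infusion at a 50% reduction in rate (i.e., 50% of rate being used at the time that the reaction occurred"). A recurrence after resumption ends the infusion. For serious or severe "hypersensitivity-like reactions (e.g., hypotension, mucosal involvement), the investigator must discuss with the Medical Monitor whether to continue study drug treatment".

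Table 1 also sets the starting rates. For a first infusion: "Begin infusion at an initial rate of 0.5 mL/min (30 mL/hr"), rising to 1.0 and then 3.0 mL/min at 30-minute steps. The same start applies after a reaction at the previous infusion. After a well-tolerated infusion, sites "begin infusion at a rate of 3.0 mL/min". Footnote a applies the first-infusion instructions again to the first infusion of the open-label extension (OLE).

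**Section 5.1.3.2.** This section separates reactions by severity. For a mild reaction: "Once the reaction has resolved, the infusion rate will be resumed at half of the most recently used rate". For a moderate to severe reaction the infusion is stopped at once, and then: "The infusion should not be restarted before all symptoms have disappeared, and then it should be restarted at half the initial rate". The section rules out resuming once a reaction recurs during that visit, and also after "mucosal tissue involvement, airway compromise, or symptomatic hypotension with systolic blood pressure" below 90 mmHg, measured supine. It also repeats the requirement for a Medical Monitor discussion.

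**The concern.** Section 5.1.3.2 itself distinguishes the most recently used rate from the initial rate, so these are not two wordings of one rule. Table 1 applies the first of them to every reaction. Section 5.1.3.2 keeps it for mild reactions and uses the second for moderate to severe ones. The conditions that rule out resuming also differ.

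If the rules give different rates for the same patient, a site cannot follow both, and patients with the same reaction may be handled differently from site to site. The infusions begun at 0.5 mL/min, where the question arises most clearly, include the first OLE infusion. For patients randomized to placebo, that is their first MTAU9937A dose in this study. Section 4.3.2 also permits dosing at home or at an approved alternate location during the pandemic, where a single clear instruction matters more.

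**Working it through.** **Inputs.** Table 1 rate steps: 0.5, 1.0 and 3.0 mL/min. Starting rates: 0.5 mL/min (first double-blind infusion, first OLE infusion, or after a reaction at the prior infusion) or 3.0 mL/min (after a well-tolerated infusion).

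**Formulas.**
- Table 1 restart = 0.5 × rate in use at the reaction.
- Section 5.1.3.2 restart, mild = 0.5 × most recently used rate.
- Section 5.1.3.2 restart, moderate to severe = 0.5 × initial rate.

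**The protocol's own example.** Section 5.1.3.2 illustrates the mild rule with a reaction at 60 mL/hr (1.0 mL/min). Half of 60 is 30 mL/hr, and half of 1.0 is 0.5 mL/min, as it states. For mild reactions the two places agree on the rate.

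**Moderate to severe reactions.** The initial rate can mean the starting rate of that infusion, or the 0.5 mL/min to which Table 1 attaches the term. For infusions begun at 0.5 mL/min the two meanings coincide.

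| Infusion begun at | Reaction at | Table 1 | Section 5.1.3.2 | Ratio |
|---|---|---|---|---|
| 0.5 | 0.5 | 0.5 × 0.5 = 0.25 | 0.5 × 0.5 = 0.25 | 1 |
| 0.5 | 1.0 | 0.5 × 1.0 = 0.50 | 0.25 | 2 |
| 0.5 | 3.0 | 0.5 × 3.0 = 1.50 | 0.25 | 6 |
| 3.0 | 3.0 | 1.50 | 0.5 × 3.0 = 1.50 (own start) | 1 |
| 3.0 | 3.0 | 1.50 | 0.25 (0.5 mL/min reading) | 6 |

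Rates are in mL/min.

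**Illustration in time.** Assume a total of 100 mL (the bag size in Section 4.3.2.1), a reaction just as a first infusion reaches 3.0 mL/min, and no later rate increase. Volume given is 30 × 0.5 + 30 × 1.0 = 45 mL, leaving 55 mL. That takes 55 / 1.5 ≈ 37 minutes under Table 1 and 55 / 0.25 = 220 minutes under Section 5.1.3.2.

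**Conditions for not resuming.**

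| Finding | Table 1 | Section 5.1.3.2 |
|---|---|---|
| Recurrence at the same visit | Do not resume | Do not resume |
| Mucosal involvement | Named only as a prompt for Medical Monitor discussion | Do not resume |
| Symptomatic hypotension, systolic below 90 mmHg | Hypotension named only as such a prompt | Do not resume |
| Airway compromise | Not mentioned | Do not resume |

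Appendix 6 says to stop the infusion for suspected anaphylaxis and does not address resuming.

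**Precedence.** Section 4.3.2.1 directs sites to Table 1 and the pharmacy manual for infusions. Sections 4.3.2 and 5.1 direct them to the Section 5.1 guidelines for adverse events. Section 5.1.1.1 presents 5.1.3.2 as supplementary, and 5.1.3.2 refers back to 4.3.2.1. None of these says which text prevails.

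**Secondary points.** Table 1 allows slowing where 5.1.3.2 requires an immediate stop. Table 1's conditions for the next starting rate can also overlap. One is any reaction at the prior infusion. The other is the absence of Grade 2 reactions at a final rate of 3.0 mL/min. A Grade 1 reaction can fit both.

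**The case against.** The strongest reply is that Table 1 is the general rule and Section 5.1.3.2 the severity-specific one. The structure gives this some support. Section 4.3.2, the parent of Table 1, sends adverse-event handling to Section 5.1.3. Within 5.1.3.2, the only reference to Section 4.3.2.1 attached to a restart rate sits in the sentence on mild reactions; the others concern the Medical Monitor discussion. This reading is reasonable, but no sentence states it, and Table 1 itself covers serious and severe reactions, so it cannot be confined to mild ones.

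A second reply is that the bars on resuming are an omission in Table 1 rather than a contradiction. That is partly right: the Medical Monitor sentence appears in both places and concerns continuing study drug, not clearly the current infusion. Even so, Table 1 tells sites to resume once a reaction resolves, without exception, and doing so after one of the three findings breaches 5.1.3.2. On stopping or slowing, the reply succeeds to this extent: a site that stops satisfies both texts.

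Third, the scope is narrow. A patient with no earlier reaction has two infusions begun at 0.5 mL/min, out of 37 scheduled doses in Cohort 1 (13 + 24) or 40 in Cohort 2 (16 + 24). The sixfold gap for infusions begun at 3.0 mL/min depends on one reading of an undefined term. The pharmacy manual, which is not among the documents, may already give a single rule. Section 1.2.2 reports no identified adverse drug reactions with MTAU9937A. These points limit the size of the problem but do not remove it.

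**Conclusion.** The concern holds. For a moderate to severe reaction at 1.0 or 3.0 mL/min in an infusion begun at 0.5 mL/min, the two passages give restart rates that differ twofold and sixfold, whichever meaning of initial rate is taken. There is no gap for a reaction at 0.5 mL/min. For infusions begun at 3.0 mL/min the ratio is 1 or 6, depending on that meaning. The passages also differ on three findings that rule out resuming, and agree on recurrence.

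The conclusion rests on the protocol text alone, with the pharmacy manual unseen. The documents give neither the frequency of infusion reactions nor the number of first OLE infusions still to come, so the number of affected infusions is not estimated. A correction would act mainly in the OLE. The ground for making it is consistent patient safety; efficacy inference is unaffected.

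**What to change.** Reconcile Table 1 with Section 5.1.3.2, or state which of them governs. After reconciliation both should give:

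- the same restart rule for each severity, with the reference rate named and initial rate defined if the term is kept;
- the same conditions for not resuming;
- conditions for the next infusion's starting rate that do not overlap.

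Check the pharmacy manual against the result. The clinical content is for the sponsor's clinical team to decide; no view is taken here on which rate or rule is right. The cost is a protocol clarification and a site notification, with no added procedures.

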5.1.3.3 Management of Increases in QT Interval

Study drug should be discontinued in patients who develop any of the following, unless there is a clear alternative cause for the changes:

- Sustained (at least two ECG measurements >30 minutes apart) QTcF that is >500 ms and >60 ms longer than the baseline value
- Sustained absolute QTcF that is >515 ms
- An episode of torsades de pointes or a new ECG finding of clinical concern

Of note, if there is a new intraventricular conduction block, the increase in QRS complex duration should be subtracted from the QTcF change, because this represents an increase in QTcF unrelated to alterations in repolarization. Also of note, it is not uncommon to record arrhythmias such as non-sustained ventricular tachycardia,

supraventricular tachycardia, pauses, or atrial fibrillation in HVs receiving placebo during periods of extended ECG monitoring. Therefore, it is critical that expert cardiology advice be sought to confirm any ECG changes and to ascertain the likelihood of a drug-induced arrhythmia versus the background occurrence of this arrhythmia. In such a situation, saving all available ECG data is highly suggested.

Management of patients with sustained QTcF prolongation should include close monitoring, with ECGs repeated at least hourly until two successive ECGs show resolution of the findings, correction of any electrolyte abnormalities, and possible discontinuation of other concomitant medications that are known to prolong the QT interval. Consultation with a cardiologist or electrophysiologist is recommended, to help in the management of such patients.

In rare circumstances, it may be acceptable to resume study drug, at a lower dose, provided that any ECG abnormalities have resolved and the patient is appropriately monitored. Clinical judgment should be applied.

